### 3 INVESTIGATIONAL PLAN

#### 3.1 General Schema of Study Design (Figure 1)

Screening and Approach: All PICU patients will be screened twice daily during weekdays, and once daily on weekends, for presence of study eligibility criteria. Patients are initially screened using an existing EPIC functionality to identify new instances of mechanical ventilations, and additional screening of potentially eligible subjects will be performed by trained research assistants and coordinators. Eligible subjects will be approached within 24 hours of meeting eligibility criteria for trial participation and informed consent.

Intervention: Intervention will start immediately after randomization, with initiation of EIT and of randomized  $\Delta P$  strategy within 4 hours of consent. The Intervention Phase will continue until either the primary outcome or failure criteria are reached, withdrawal from the study, death, or 90 days from randomization.

Follow-Up: Follow-up will start once the Intervention Phase is finished and will continue until hospital discharge or 90 days post-randomization, whichever comes first.

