Ancillary therapy documentation	Required	While the order of use, or the decision to use, the above therapies are not mandated, all ancillary therapy use will be recorded daily
Ventilator weaning (may occur after Intervention Phase)	CHOP Ventilator Weaning Pathway	The CHOP PICU ventilator weaning pathway is initiated when there is spontaneous breathing, PEEP $<$ 12 cmH 2 O and FIO 2 $<$ 0.50; the pathway reduces respiratory rate, PEEP, and pressure support every 4 hours as tolerated until extubation readiness test
Extubation readiness (may occur after Intervention Phase)	CHOP ERT pathway (embedded in Ventilator-Weaning Pathway)	A spontaneous breathing trial (PEEP $\leq$ 8 cmH 2 O and pressure support $\leq$ 8 cmH 2 O for 1 to 2 hours) is initiated when PEEP $\leq$ 8 cmH 2 O and FIO 2 $\leq$ 0.40; an endotracheal tube leak is assessed and dexamethasone recommended for leak $>$ 20 cmH 2 O; subjects who pass this trial are extubated within 6 hours

**Electrical Impedance Tomography (EIT):** EIT is an FDA-approved non-radiating method of imaging lung aeration currently used at CHOP for clinical care, with an associated existing EPIC order. For PARMA, EIT will be performed post-randomization after stabilization of settings on the assigned  $\Delta P$  study arm and no later than 8 hours after initiation of assigned protocol. EIT measurements will be repeated 24 to 72 hours after initial post-randomization EIT measurements while on the assigned ventilator protocol. If the subject is off of the assigned protocol (i.e., failure criteria or early termination), the repeat EIT will be deferred. EIT images will not routinely be made available to the clinical team, as they require some significant offline processing.

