## 5 STUDY EVALUATIONS AND MEASUREMENTS

### 5.1 Screening and Monitoring Evaluations and Measurements

#### 5.1.1 Medical Record Review

Detailed clinical data will be recorded, including demographics (age and sex), severity of illness (Pediatric Risk of Mortality [PRISM] IV; Pediatric Logistic Organ Dysfunction [PELOD] 2), co-morbidities (prematurity, immunocompromised status, stem cell transplant), and ARDS etiology (e.g., pneumonia, sepsis, trauma, aspiration). Pre- and post-randomization ventilator settings, oxygenation, ancillary therapy use, and adverse events will be documented daily until discontinuation of invasive ventilator support. Organ failures (PELOD 2 score derived from labs), vasopressor support, and clinical outcomes will be monitored until hospital discharge. REDCap will serve as the data collection interface.

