### 5.2 Efficacy Evaluations

The primary outcome (Aim 1A) of PARMA is time to sustained resolution of hypoxemia, defined as being alive with PaO2/FIO2 > 300 (or SpO2/FIO2 > 315) on two consecutive measurements 4 hours apart. This is because improved oxygenation is strongly associated with outcome in pediatric ARDS, and is the most plausible mechanism for the efficacy of a high ΔP strategy, both for composite outcomes such as VFDs (by shortening invasive ventilator duration and avoidance of rescue therapies), as well as mortality (improved organ function via improved gas exchange and reduced morbidity associated with prolonged ventilation). This outcome is censored at 28 days (672 hours).

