## 6 STATISTICAL CONSIDERATIONS

### 6.1 Primary Endpoint

The primary outcome (Aim 1A) of PARMA is time to sustained resolution of hypoxemia, defined as being alive with  $\text{PaO}_2/\text{FIO}_2 > 300$  (or  $\text{SpO}_2/\text{FIO}_2 > 315$ ) on two consecutive measurements 4 hours apart. This is because improved oxygenation is strongly associated with outcome in pediatric ARDS, and is the most plausible mechanism for the efficacy of a high  $\Delta P$  strategy, both for composite outcomes such as VFDs (by shortening invasive ventilator duration and avoidance of rescue therapies), as well as mortality (improved organ function via improved gas exchange and reduced morbidity associated with prolonged ventilation). This outcome is censored at 28 days (672 hours).

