#### 6.3.2 Efficacy Analysis

PARMA will be analyzed using Bayesian survival analyses, with effect size presented as a hazard ratio (HR). All analyses will be “intention to treat.” The main analysis will use a minimally informative prior centered at  $\text{HR} = 1$  ( $\log[\text{HR}] = 0$ ) and precision = 10 (log scale). The primary outcome of hypoxemia resolution (Aim 1A) will be assessed as a time to event (in hours) from randomization until the primary event of hypoxemia resolution. Subjects who die before hypoxemia resolution will remain in the risk set and be considered as being “never able to achieve hypoxemia resolution” (effectively being treated as a competing risk). Subjects who achieve hypoxemia resolution and die subsequent to that will be considered as having achieved the primary outcome. The high  $\Delta P$  (comparator) arm will be compared to the low  $\Delta P$  (reference) arm, and efficacy reported as HR with 95% credible intervals. Posterior probabilities under minimally informative priors will be computed for any benefit ( $\text{HR} > 1$ , meaning faster time to hypoxemia resolution with high  $\Delta P$ ),

HR > 1.25, and HR > 1.5 (projected “true” effect size). Additional analyses will be conducted with standardized priors reflecting pessimistic (priors centered at HR 0.8) and optimistic (priors centered at HR 1.2) scenarios, as we have done before. As this is the first trial of different  $\Delta P$  ventilation strategies on hypoxemia resolution in pediatric ARDS, reasonable data-driven priors from previous publications, including adult trial data, were not available. The standardized prior framework (minimally informative, pessimistic, optimistic) reflects a range of plausible priors with the same precision under which the PARMA trial data can be adjusted to derive posterior probabilities.

For Aim 1B, we will assess whether the effect size of high versus low  $\Delta P$  ventilation differs according to age (continuous in years and as strata of < 1 year, 1 to < 5 years, 5 to < 12 years, and 12 to 18 years), pre-randomization elastance ( $\Delta P/V_T$  with  $V_T$  normalized to IBW), and pre-randomization  $\text{PaO}_2/\text{FIO}_2$ .

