### **9.2 Data Collection and Management**

Detailed clinical data will be recorded, including demographics (age and sex), severity of illness (Pediatric Risk of Mortality [PRISM] IV; Pediatric Logistic Organ Dysfunction [PELOD] 2), co-morbidities (prematurity, immunocompromised status, stem cell transplant), and ARDS etiology (e.g., pneumonia, sepsis, trauma, aspiration). Pre- and post-randomization ventilator settings, oxygenation, ancillary therapy use, and adverse events will be documented daily until discontinuation of invasive ventilator support (i.e., extubation or removal of ventilator for subjects with tracheostomy). Organ failures (PELOD 2 score), vasopressor support, and clinical outcomes will be monitored until hospital discharge or 90 days, whichever is sooner. REDCap will serve as the data collection interface, and will require password-protected access.

Site investigators and research staff will be trained to collect data using electronic case report forms (CRFs). The CRF will be password-protected with safeguards to maintain confidentiality for all data entered into the CRF.

An electronic Manual of Operations (MOO) describing Standard Operating Procedures (SOP) for data collection will be prepared to ensure consistent documentation. The PICU research team will maintain an enrollment log that will link each potential subject to a unique study number. All data collection forms will contain this unique study number. Enrollment logs will be maintained by the PICU research team in a secure location accessible to study staff only. Identifiable information will be collected and stored locally, but no identifiable information will be transmitted to the Data Coordinating Center (DCC) at Penn. All data received at the DCC will be coded using a subject ID.

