**Retention:** The research team will be extensively trained in the screening process, eligibility criteria, and in study procedures. PARMA will be advertised to the CHOP PICU faculty, nurses, and respiratory therapists via multiple existing venues, including research conferences and weekly operational meetings. Aspects of the PARMA protocol that are congruent with existing ventilation practices at CHOP will be emphasized in order to facilitate acceptance and adherence. Compliance with assigned treatment group, adherence to ventilator protocol, and adherence to protocolized co-interventions will be monitored. The intervention will not be blinded to clinicians or investigators as blinding ventilator management is neither feasible nor safe in critically ill children. We will provide targeted intervention to study staff if enrollment drops < 50% consent of eligible subjects and if protocol adherence falls < 70%. Subjects who meet failure criteria will continue to have data recorded, and subjects who are withdrawn due to family request will be asked whether data can still be collected. Primary, secondary, and safety endpoints will be monitored and determined through hospital discharge or 90 days post-randomization, which will minimize loss to follow-up.

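### Oxygenation recording stops at extubation, yet the primary endpoint needs oxygenation readings up to day 28 whatever the ventilation status

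*Protocol*

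**What the plan says.** **Recording.** Protocol 5.1.1 states: "Pre- and post-randomization ventilator settings, oxygenation, ancillary therapy use, and adverse events will be documented daily until discontinuation of invasive ventilator support". Section 9.2 repeats this and defines the stopping point: "until discontinuation of invasive ventilator support (i.e., extubation or removal of ventilator for subjects with tracheostomy". Both sections follow organ failure, vasopressor support and clinical outcomes for longer, to hospital discharge (9.2 adds a 90-day limit).

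**Endpoint.** Sections 5.2 and 6.1 define resolution as being alive with PaO2/FIO2 above 300, or SpO2/FIO2 above 315, on two readings 4 hours apart. No condition refers to the ventilator. Section 6.1 adds: "This outcome is censored at 28 days (672 hours".

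**Ascertainment window.** Section 9.5 states: "Primary, secondary, and safety endpoints will be monitored and determined through hospital discharge or 90 days post-randomization". Section 4.3 continues data gathering to discharge, up to 90 days, and Table 1 lists the primary outcome to day 28.

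**Scoring.** Section 6.3.2 analyses by intention to treat. For death it says: "Subjects who die before hypoxemia resolution will remain in the risk set". Death after resolution counts as an event. Leaving ventilation alive before resolution is not mentioned.

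**Phases.** Section 3.1: "The Intervention Phase will continue until either the primary outcome or failure criteria are reached, withdrawal from the study, death, or 90 days from randomization". Extubation is not on that list. In section 3.1.2, pressure support is tied to the assigned ΔP during the Intervention Phase and weaned in Follow-Up. The extubation readiness row, labelled as something that may occur after the Intervention Phase, ends: "subjects who pass this trial are extubated within 6 hours".

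**The concern.** The recording rule and the endpoint need different data. If oxygenation stops being recorded when the tube comes out, a child extubated before the second qualifying reading can never be shown to have resolved, although 9.5 says the endpoint is still being determined. Such a child may be recovering well.

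Intention to treat keeps that child in the primary analysis, so some score has to be given. Leaving the child at risk to 672 hours as unresolved treats a possible recovery like a death. Censoring at extubation removes children who may be about to resolve. Either choice costs power, and if the arms are affected unequally, either shifts the hazard ratio.

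**Working it through.** **1. Does the extubation rule imply the endpoint?** The SpO2 target is 92 to 97% and the breathing trial may start at FIO2 ≤ 0.40 (both section 3.1.2). SpO2/FIO2 is then:

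- FIO2 0.40: 92/0.40 = 230 to 97/0.40 = 242.5. PaO2/FIO2 above 300 would need PaO2 above 120.
- FIO2 0.30: 92/0.30 = 307 to 97/0.30 = 323, so the criterion can be met.
- Largest FIO2 that can meet it within the target: 97/315 = 0.308.
- Room air: 92/0.21 = 438.

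A child can therefore satisfy the readiness threshold without satisfying the endpoint, and readings after extubation would often settle the matter if they were recorded.

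**2. Who can take that path?** Pressure support follows the assigned ΔP (10 to 20 or 20 to 30 cmH2O) until the Intervention Phase ends, and the breathing trial runs at ≤ 8. An adherent child should therefore resolve before planned extubation. The remaining routes are failure criteria (which end the Intervention Phase under 3.1, with later ventilation at the physician's discretion under 4.3), early termination, unplanned extubation, and early weaning.

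**3. The plan's own figure.** Section 6.4: N = 160, HR 1.5, prior precision 10 on the log scale, success if P(HR > 1) > 0.90, power 80%, type I error 0.07. The event count is not printed. With d events, information I = d/4 and estimated log hazard ratio b:

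- success if I·b/√(10 + I) > 1.2816
- type I error = 1 − Φ(1.2816·√((10 + I)/I))
- power = Φ(ln 1.5·√I − 1.2816·√((10 + I)/I))

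Assume 75% resolve by day 28 in the low arm. At HR 1.5 the high arm has 1 − 0.25^1.5 = 87.5%, so d = 80 × 0.75 + 80 × 0.875 = 130 and I = 32.5. Then 1.2816 × √(42.5/32.5) = 1.466, type I error = 0.071, and power = Φ(0.4055 × 5.701 − 1.466) = Φ(0.846) = 0.80. The stated design is reproduced.

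**4. Effect of missing readings.** 4,000 simulated trials per scenario; non-resolvers stay in the risk set to day 28. A share q of true resolvers, chosen at random, loses the qualifying readings. Censoring is placed at the time the event would have occurred. The protocol gives no value for q, so a range is shown.

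| q, both arms | Scoring | HR (true 1.5) | Power | Type I error (true HR 1) |
|---|---|---|---|---|
| 0% | – | 1.50 | 0.80 | 0.077 |
| 5% | non-event | 1.45 | 0.71 | 0.067 |
| 10% | non-event | 1.41 | 0.65 | 0.065 |
| 20% | non-event | 1.36 | 0.51 | 0.062 |
| 5% | censored | 1.51 | 0.78 | 0.067 |
| 10% | censored | 1.50 | 0.76 | 0.060 |
| 20% | censored | 1.51 | 0.72 | 0.059 |

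The Monte Carlo standard error near 0.07 is √(0.07 × 0.93/4000) = 0.004, so type I error is essentially unchanged.

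Unequal shares:

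- 10% low, 5% high, true HR 1: non-event scoring gives HR 1.10 and type I error 0.16; censoring gives 1.06 and 0.11.
- 5% low, 10% high, true HR 1.5: non-event scoring gives HR 1.29 and power 0.46; censoring gives 1.43 and 0.68.

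**The case against.** **The pressure-support hold closes the path.** This largely stands for adherent children, and the readiness row is labelled as following the Intervention Phase. A reader might infer from the FIO2 ≤ 0.40 trigger that extubation before resolution is routine; the protocol does not support that. The hold does not cover failure, early termination or unplanned extubation, and the word may in the label leaves early weaning unsettled.

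**No text scores an extubated child as a non-event.** This stands. A reader might infer that recovered children count as unresolved to day 28, but the never-resolves rule in 6.3.2 is written for deaths only. Censoring is also possible, and taken literally the endpoint would accept readings after extubation.

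**The daily recording sentence cannot be the only source of an endpoint timed in hours.** This is fair, and 4.3, 9.5 and Table 1 suggest the intention is to keep looking. But 5.1.1 and 9.2 are explicit about when oxygenation stops, and 9.2 gives longer follow-up to other items in its next sentence. The conflict remains.

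**Scoring belongs to the analysis plan, which is not shown.** This is partly right: the absence of a detailed scoring rule would not be a finding by itself. However, an analysis plan cannot score readings that the protocol says are not collected.

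**Imbalance between arms is speculative.** The different pressure-support levels do not show it: if the hold is obeyed, both arms sit above 8 cmH2O, and if it is not, the argument lapses. Section 4.3 names respiratory acidosis as a failure trigger and 9.4.2 considers acidosis plausible with low ΔP, but 9.4.2 also names air leak with high ΔP. The direction is not established.

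**Conclusion.** The contradiction is real. Sections 5.1.1 and 9.2 stop collecting the only data from which the primary endpoint is built, at a point before 4.3, 9.5 and Table 1 say its determination ends. It affects children who leave invasive ventilation alive before resolution, probably a minority if the ventilator protocol is followed.

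The size is conditional. It rests on an assumed 75% resolution in the low arm, on affected children being a random share of resolvers, and on q, which the protocol does not give. With equal shares of 5 to 20%, power drops to about 0.71 to 0.51 (non-event) or 0.78 to 0.72 (censored), and no false positives are added. With unequal shares the bias can run either way; a 10% against 5% split scored as non-events would take type I error to about 0.16, beyond the ceiling of 0.1 in section 6.4. It would go too far to conclude that the stated 80% power is lost or that the hazard ratio is distorted: N = 160 reproduces as planned, and the loss need not arise if readings continue.

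**What to change.** - **5.1.1 and 9.2:** record SpO2/FIO2 (or PaO2/FIO2) for the primary endpoint until resolution or 672 hours regardless of ventilation status, within the hospital follow-up that 9.5 already sets.
- **6.1 and 6.3.2:** state that a child extubated before the event stays at risk and is scored on the same two-reading criterion from readings after extubation, with FIO2 taken as 0.21 on room air. Extubation itself is neither a censoring time nor a non-event.
- **Reporting:** give by arm the number extubated before the event.
- **3.1 and 3.1.2:** reconcile the end of the Intervention Phase, the pressure-support row and the weaning and extubation rows on whether weaning and extubation may precede the primary outcome. Which clinical rule applies is for the investigators.

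The cost is protocol and case report form wording plus chart extraction for a limited period after extubation. One drawback remains: delivered FIO2 on low-flow support is uncertain, so some events may be dated slightly late.

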As per NICHD practices, the DSMB recommendations will be signed and submitted to the NICHD officer (who is usually the Executive Secretary for the DSMB) within a reasonable time after the DSMB meeting. After approval or modification by the NICHD, the officer will forward the DSMB report to the PI, who will forward to the IRB. In the unlikely event that the DSMB recommends emergent cessation of enrollment in PARMA because of safety concerns, this communication will be made during the debriefing segment of the DSMB meeting. If the NICHD staff concur with this recommendation, the PI will notify all PARMA-related investigators and staff to cease enrollment immediately.

---

TABLE 1: SCHEDULE OF STUDY PROCEDURES

Study Phase	Enrollment Window	Randomization (≤ 4 hours of consent)	Treatment Protocol		Follow-up		
			1	2	3	4	5
Visit Number	0	1	1	2	3	4	5
Study Days	1	1	1	2-3	1-28	1-90	1-90
Informed Consent/Assent	X						
Review Inclusion/Exclusion Criteria	X						
Demographics/Medical History	X						
Vital Signs: BP, HR, RR (medical record)	X						
Height and Weight (medical record)	X						
Prior/Concomitant Medications	X						
Clinical Laboratory Evaluation	X						
Randomization		X					
Ventilator protocol			X	X	X	X	X
EIT protocol			X	X			
Protocol Compliance		X	X	X	X	X	X
Primary outcome to day 28					X		
Hospital discharge						X	
90 days after randomization (if not discharged)							X
Adverse Event Assessment			X	X	X	X	X
Discontinuation of Ventilation Protocol							
Withdrawal from Study							

[figure not shown]

FIGURE 1: STUDY DIAGRAM

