### **6.3.3 Safety Analysis**

The frequencies of AEs by type, body system, severity and relationship to study intervention will be summarized. SAEs (if any) will be described in detail.

AE incidence will be summarized along with the corresponding exact binomial 95% two-sided confidence intervals.

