## 8 SAFETY MANAGEMENT

### 8.1 Clinical Adverse Events

Clinical adverse events (AEs) will be monitored throughout the study, daily during the intervention phase.

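### Sections 5.1.1 and 9.2 end adverse-event recording when invasive ventilation stops, while Table 1 and sections 4.3, 8.1 and 9.5 run to discharge or day 90; under the shorter rule, events after extubation are lost over a window that can differ by arm

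*Protocol*

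**What the plan says.** **Shorter rule.** Section 5.1.1 states that "adverse events will be documented daily until discontinuation of invasive ventilator support". Section 9.2 repeats this and defines the end point: "adverse events will be documented daily until discontinuation of invasive ventilator support (i.e., extubation or removal of ventilator for subjects with tracheostomy". In both sections the next sentence lists what is followed further, namely organ failure scores, vasopressor support and clinical outcomes. AEs are not in that list.

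**Longer rule.** Table 1 has a row "Adverse Event Assessment" with five marks, which line up with the treatment and follow-up visits 1 to 5; the last two columns cover study days 1 to 90. Section 8.1 says: "Clinical adverse events (AEs) will be monitored throughout the study, daily during the intervention phase". Section 9.5 (Retention) says: "Primary, secondary, and safety endpoints will be monitored and determined through hospital discharge or 90 days post-randomization". Section 4.3 continues data gathering to discharge, up to 90 days. Section 8.3 requires all AEs on the case report form and names no cut-off.

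**Daily period.** Section 8.1 ties daily monitoring to the Intervention Phase. Section 3.1 ends that phase at the primary outcome, failure criteria, withdrawal, death or day 90. Extubation is not on the list, and section 3.1.2 notes that weaning and extubation may come after the phase.

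**Analysis.** Section 6.3.3: "AE incidence will be summarized along with the corresponding exact binomial 95% two-sided confidence intervals". No period is named there.

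**The concern.** Sections 5.1.1 and 9.2 describe what staff enter in REDCap, so the shorter rule could be the one that is followed. It ends at a post-randomization event that treatment is expected to move. Sections 5.2 and 6.1 give shorter invasive ventilation as a route by which high ΔP would work, and section 9.4.2 says high ΔP could shorten time on the ventilator.

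Under that rule, an AE after extubation is not captured unless it falls under another followed outcome, and the arm extubated sooner is observed for less time. A binomial proportion takes no account of this. Tolerability and safety of high ΔP is a secondary objective (section 2.2), section 9.4.2 names pneumothorax and other air leak as plausible harms of that arm, and section 4.4 gives no explicit stopping rules and relies on DSMB review of AEs. A later analysis plan can choose a window or an exposure adjustment, but it cannot recover events that were never collected.

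**Working it through.** **1. Passages side by side**

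| Place | Daily recording ends | AE recording ends |
|---|---|---|
| 5.1.1, 9.2 | End of invasive ventilation | No later recording stated |
| 8.1 with 3.1 | End of Intervention Phase | Throughout the study |
| Table 1 | Not stated | Visits to day 90 |
| 4.3, 9.5 | Not stated | Discharge or day 90 |

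Both columns disagree. Even if the wording in 5.1.1 and 9.2 sets only a frequency, the daily period still ends at a different event in 8.1.

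**2. Which events are exposed** (event table in section 8.6, with 5.1.1 and 9.2)

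- Death: a clinical outcome, followed to discharge. Protected.
- New or progressive multiple organ dysfunction: defined at 7 days after randomization, with organ scores followed to discharge. Protected.
- Vasopressor increase for acidosis: vasopressor support is followed to discharge. Largely protected.
- Ventilator-associated pneumonia and protocol termination for failure: bound to ventilation or to the protocol. Little affected.
- Pneumothorax or other air leak after extubation, thrombosis or embolus, arrhythmia, new seizures: exposed.

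**3. Size, as an illustration.** The protocol gives no figure to reproduce. Every input here is an assumption.

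- First-AE hazard L per day, equal in both arms and equal on and off the ventilator, set to give a 28-day risk R of 10%, 20% or 30%: L = −ln(1 − R)/28.
- Exponential ventilation time, low-arm median 7, 10 or 14 days: m = ln 2/median. High-arm extubation rate is 1.5m.
- Recorded incidence when counting stops at extubation or day 28: P(m) = L/(L + m) × [1 − exp(−28(L + m))].

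Worked case, R = 20%, median 10 days: L = 0.22314/28 = 0.00797 and m = 0.06931.

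- Low arm: L + m = 0.07728; 0.00797/0.07728 × (1 − exp(−2.164)) = 0.1031 × 0.8851 = 9.1%.
- High arm: L + 1.5m = 0.11194; 0.00797/0.11194 × (1 − exp(−3.134)) = 0.0712 × 0.9565 = 6.8%.
- Ratio: 0.0681/0.0913 = 0.75. With 80 per arm (160/2), that is 7.3 versus 5.4 subjects.
- Common 28-day window: 20% in each arm (16 of 80), ratio 1.00.

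Recorded ratio, high/low:

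| Low-arm median | R = 10% | R = 20% | R = 30% |
|---|---|---|---|
| 7 days | 0.705 | 0.711 | 0.717 |
| 10 days | 0.741 | 0.746 | 0.752 |
| 14 days | 0.782 | 0.786 | 0.791 |

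**4. Sensitivity.** Without the day-28 limit, P = L/(L + m). For L of 0.005 to 0.05 per day and a low-arm mean of 7 to 14 days, the ratio is 0.67 to 0.77 at an extubation rate ratio of 1.5 and 0.81 to 0.87 at 1.25. The distortion shrinks as the difference in extubation shrinks.

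**5. What could be hidden.** In the worked case, a true AE hazard ratio of 1.37 against high ΔP gives L = 0.01092 and a recorded incidence of 9.1% in the high arm, the same as the low arm.

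**The case against.** The strongest reply is that the document largely settles the matter. Sections 5.1.1 and 9.2 carry one sentence, not two independent rules; it governs a list that opens with ventilator settings; and *daily until* may set only how often the bedside is reviewed. Section 8.1 separates frequency from duration, 9.5 names the window for safety endpoints, 8.3 puts all AEs on the case report form without a cut-off, and 9.2 leaves collection procedures to a Manual of Operations. This reading is available, so it cannot be said that the protocol chose a safety analysis ending at extubation. But 5.1.1 and 9.2 state no later AE recording, they list what does continue without AEs, and their daily period differs from that in 8.1. The passages still have to be reconciled.

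A reader might infer that every safety event is under-counted in the high ΔP arm. The documents do not support this: most pre-specified safety outcomes are followed separately or are bound to ventilation or to the protocol. Fewer ventilator-related events because ventilation was shorter would also be a genuine effect of treatment, which section 9.4.2 anticipates, and not a bias.

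A reader might also take the ratios as the expected bias in this trial. The only hazard ratio of 1.5 in the protocol is for hypoxemia resolution (section 6.4), and applying it to extubation is an assumption. Where the AE hazard falls after extubation, as is likely for air leak, the distortion is smaller.

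Finally, the absence of a window in 6.3.3 is not in itself an error, since that detail may sit in an analysis plan. What stands is the contradiction about what is collected.

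**Conclusion.** The contradiction is real and should be removed. Followed as written, sections 5.1.1 and 9.2 would lose AEs that arise after ventilation and outside the separately followed outcomes, and the window for those events would be shorter in whichever arm is extubated sooner. By the protocol's hypothesis that is high ΔP, the arm whose safety is in question. Crude incidence would then not be comparable between arms for these events.

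The recorded ratio of about 0.71 to 0.79 in place of 1.00 is conditional on an extubation hazard ratio of 1.5, low-arm median ventilation of 7 to 14 days, and an AE hazard that is constant, equal between arms and equal on and off the ventilator. If the hazard is no higher off the ventilator than on it, these ratios bound the distortion from above. They do not apply to death, organ dysfunction, vasopressor use, ventilator-associated pneumonia or protocol failure. If staff already record AEs to discharge or day 90, as 8.1 and 9.5 imply, there is no loss and only the wording needs correction.

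**What to change.** 1. In sections 5.1.1 and 9.2, state that AEs and SAEs are recorded from randomization to hospital discharge or day 90, whichever comes first, regardless of ventilation status. This matches Table 1, 8.1 and 9.5.
2. Let only the daily frequency end earlier, and at the same stated event in 5.1.1, 9.2 and 8.1.
3. In section 6.3.3, report AE incidence by arm over one common period counted from randomization, for example through day 28, and not ended by extubation. Use the same period for all AEs and SAEs: most pre-specified safety outcomes are also SAEs in the section 8.6 table, so separate windows would overlap.
4. Note in 6.3.3 that events after discharge are not captured. Discharge is itself a post-randomization event and may differ by arm, so collection to discharge or day 90 is not a fixed window.

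The cost is a wording amendment and some extra chart review after extubation. Subjects are already followed to discharge or day 90 for other outcomes.
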